### 10.5 VITAL SIGNS

Descriptive statistics for systolic blood pressure (mm Hg), diastolic blood pressure (mm Hg), pulse rate (bpm), temperature (°C), height (cm), and weight (kg) will be presented by study visit and treatment group visit for each study part. Also, changes in these vital signs from baseline to each subsequent visit will be tabulated by dose level for each study part. Note that height is only collected at Screening and at the beginning of each cycle of treatment.

A Listing of vital signs will also be provided.

### 10.6 ELECTROCARDIOGRAMS

Subjects will have ECG measured at Screening and on Cycle 1, Day 8. Subjects with normal ECGs do not need to have subsequent ECGs. ECG parameters [Heart Rate (bpm), RR (msec), PR (msec), QRS (msec), QT (msec), and QTcF (msec)] collected. These ECG findings will be summarized with frequencies and percentages by dose and time point. ECG results will also be categorized as 'Normal', 'Abnormal, Not Clinically Significant', or 'Abnormal, Clinically Significant' and any clinically significant abnormalities described.

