### **QTc Prolongation**

The balance of preclinical evidence suggests BVD-523 has low, but observable, potential to cause QT prolongation. Due to potentially unique species sensitivity, as well as possibly unknown consequences following chronic dosing, patients dosed with BVD-523 in the first-in-human study, BVD-523-01, are being monitored for potential QTc prolongation and related cardiotoxicities via Holter monitoring. No clinically significant cardiac abnormalities have been seen to date in the first trial (BVD-523-01). QTc assessment will be performed at baseline and on Day 8, at steady state.

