## 4.3 INCLUSION CRITERIA

Patients eligible for inclusion in this trial must fulfill all of the following criteria:

- 1. Provide signed and dated informed consent prior to initiation of any study-related procedures that are not considered Standard of Care (SOC).
- 2. Male or female patients aged  $\geq$  18 years.
- 3. Have either of the following diagnoses:
  - Morphologically confirmed AML (except acute promyelocytic leukemia (APL)) including leukemia secondary to prior therapy (e.g., chemotherapy, XRT) or antecedent hematologic disorder (e.g., MDS or myeloproliferative disorders), who have failed to achieve complete remission (CR) or who have relapsed after prior therapy and are not candidates for potentially curative therapy.
  - Intermediate-2 or High-grade risk MDS (including chronic myelomonocytic leukemia (CMML)).
- 4. Have received at least one prior therapy. Patients who are over age 65 and have not received therapy for AML are also eligible, if they are not candidates for induction chemotherapy.
- 5. ECOG performance status of 0 (fully active, able to carry out all pre-disease activities without restriction) to 2 (ambulatory and capable of all self-care but unable to carry out

any work activities. Up and about more than 50% of waking hours), measured within 72 hours before the start of treatment.

- 6. Predicted life expectancy of  $\geq$  3 months.
- 7. Adequate renal function [creatinine  $\leq$  1.5 times ULN (upper limit of normal)] or GFR of  $\geq$  50mL/min.
- 8. Adequate hepatic function [total bilirubin  $\leq 1.5 \times \text{UNL}$ ; AST (aspartate transaminase) or ALT (alanine transaminase)  $\leq 3 \times \text{UNL}$  or  $\leq 5 \times \text{UNL}$  if due to liver involvement by tumor].
- 9. Adequate cardiac function,  $\geq$  institutional lower limit of normal, e.g., left ventricular ejection fraction (LVEF) of  $\geq$  50% as assessed by multi-gated acquisition (MUGA) or ultrasound/echocardiography (ECHO); corrected QT interval (QTc) < 470 ms.
- 10. Contraception:
  - For women: Negative pregnancy test for females of child-bearing potential; must be surgically sterile, postmenopausal (defined as no menstrual cycle for at least 12 consecutive months), or compliant with an acceptable contraceptive regimen (oral contraceptives, condom with spermicide etc.) during and for 3 months after the treatment period. Abstinence is not considered an adequate contraceptive regimen.

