### 6.6 STATISTICAL NOTATION AND METHODOLOGY

Unless stated otherwise, the term "descriptive statistics" refers to the number of subjects (n), mean, median, standard deviation (STD), minimum (min), and maximum (max) for continuous data and frequencies and percentages for categorical data. Min and max values will be rounded to the precision of the original value, means and medians will be rounded to 1 decimal place greater than the precision of the original value, and STDs will be rounded to 2 decimal places greater than the precision of the original value. Percentages will be rounded to the nearest whole number (zeroes are not displayed) with values of "< 1%" and "> 99%" shown as necessary for values falling near the boundaries. P-values will be presented with 3 decimal places and values less than 0.001 will be presented as < 0.001.

Unless otherwise noted, all data collected during the study will be included in data listings and will be sorted by study part (Part 1 or Part 2), subject number, and then by date/time for each subject number. For Part 2, subjects will additionally be sorted by RAS mutation status.

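### SAP 10.6 plans only frequencies and percentages for continuous ECG intervals, QTcF included, and commits to no change from baseline

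*SAP*

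**What the plan says.** SAP 10.6 fixes the time points: "Subjects will have ECG measured at Screening and on Cycle 1, Day 8". It then lists the measurements: "ECG parameters [Heart Rate (bpm), RR (msec), PR (msec), QRS (msec), QT (msec), and QTcF (msec)] collected". All six are numerical, in bpm or msec. The summary rule follows directly: "These ECG findings will be summarized with frequencies and percentages by dose and time point". The next sentence adds a second output: "ECG results will also be categorized as 'Normal', 'Abnormal, Not Clinically Significant', or 'Abnormal, Clinically Significant", with clinically significant abnormalities to be described.

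The protocol explains why the ECGs are taken. Section 1.5.1 has a heading for QTc prolongation, where it states: "The balance of preclinical evidence suggests BVD-523 has low, but observable, potential to cause QT prolongation". The same paragraph commits to a comparison: "QTc assessment will be performed at baseline and on Day 8, at steady state".

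SAP 6.6 sets the default meaning of descriptive statistics: n, mean, median, SD, minimum and maximum "for continuous data and frequencies and percentages for categorical data". SAP 14.3.4 lists two ECG tables for Part 2 by title only: 14.3.5.3.1 (Electrocardiogram) and 14.3.5.3.2 (Categorized Electrocardiogram). SAP 14 places the table examples in a separate attachment.

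**The concern.** Counts and percentages suit the Normal/Abnormal classification. They do not suit a millisecond variable unless cut-offs are given, and SAP 10.6 gives none. A programmer following the text would have to invent bins or depart from the text. Neither route leads by plan to a mean QTcF at Day 8 or a mean shift from the pre-treatment value.

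At stake is the one systematic look at QTc in this trial. The schedule of assessments (Protocol Table 6.3) has ECGs at screening and Day 8 only. Patients whose Cycle 1 ECG is normal need no repeat. The Holter monitoring described in the protocol belongs to the earlier study, BVD-523-01. A drug-related shift too small for investigators to mark individual tracings as clinically significant would appear only in a summary of the interval values, and the text does not commit to one.

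**Working it through.** The documents give no figure for the ECG analysis, so there is none to reproduce. The check compares sections and then asks how informative the missing estimate would be.

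**Step 1: which data the frequency rule covers.** The rule in SAP 10.6 comes straight after the list of six parameters and refers to these findings. The three-level classification comes afterwards and is introduced as an addition. The natural reading is that frequencies and percentages apply to the parameters themselves.

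**Step 2: comparison with the rest of the plan.**

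| Section | Data | Continuous summary stated | Change from baseline stated |
|---|---|---|---|
| SAP 10.4 | Laboratory tests | Yes | Yes |
| SAP 10.5 | Vital signs | Yes | Yes |
| SAP 10.6 | ECG intervals | No | No |

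SAP 7.2 defines baseline and change from baseline in general terms but does not assign the change to ECG. Protocol 10.3.8 names physical examinations, vital signs and clinical laboratory analyses as the safety variables to be summarised. ECG is not among them, so the protocol does not fill the gap.

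**Step 3: whether the data would support the summary.** Yes. QTcF is collected, and each patient with both ECGs has a screening and a Day 8 value. Screening is the only scheduled pre-treatment ECG, so it is normally the baseline under SAP 7.2.

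**Step 4: precision of a mean QTcF change.** Half-width of the 95% confidence interval = t(0.975, n−1) × SD / √n. The documents give no SD of change, so 10 to 25 ms is an assumption. The values of n are Part 1 cohorts of 3 and 6 (Protocol 3.1.2), a Part 2 group of 20, and both Part 2 groups together (40; SAP 4). All assume complete pairs.

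| n | t | SD 10 | SD 15 | SD 20 | SD 25 |
|---|---|---|---|---|---|
| 3 | 4.303 | 24.8 | 37.3 | 49.7 | 62.1 |
| 6 | 2.571 | 10.5 | 15.7 | 21.0 | 26.2 |
| 20 | 2.093 | 4.7 | 7.0 | 9.4 | 11.7 |
| 40 | 2.023 | 3.2 | 4.8 | 6.4 | 8.0 |

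Half-widths are in ms. For example, with n = 20 and SD 15: 2.093 × 15 / √20 = 7.0 ms. A Part 2 group would give a usable descriptive estimate. A single Part 1 cohort would not.

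**The case against.** The strongest reply is that the plan may already contain the summary. Table 14.3.5.3.1 is separate from the categorized table, so its shell could well hold means and changes. This cannot be excluded, because the shells are not in the documents. But a title commits to nothing. If the shell does hold continuous statistics, it disagrees with SAP 10.6 and the text still needs correcting.

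Other points also stand. ECGs are listed by patient, so no data are lost. A clinically relevant prolongation could be reported as an adverse event and tabulated by grade and dose level. The protocol rates the QT potential as low and reports no clinically significant cardiac abnormality so far in BVD-523-01. The trial is uncontrolled, Day 8 is not an intensive pharmacokinetic sampling day, and neither post-dose timing nor replicate ECGs are specified. A mean shift would therefore be only weakly attributable to drug. These points limit the weight of the issue, but none of them makes a frequency table the right summary for msec data.

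Four stronger readings are tempting and are not supported:

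- **The analysis cannot show a QTc effect.** The values are collected and listed, so a summary can be produced at any time. The text simply does not plan one.
- **Normal/Abnormal is the only other output.** There is a second ECG table, a listing, and a description of clinically significant abnormalities.
- **SAP 10.6 contradicts SAP 6.6.** SAP 6.6 allows departures where another section says so. SAP 10.6 is out of line with the default, without a stated reason.
- **The plan rules out counting patients above the entry limit.** Such a count is itself a frequency. The entry limit, "corrected QT interval (QTc) < 470 ms", is an eligibility rule with no correction formula named, and the documents never use it as an on-treatment threshold.

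**Conclusion.** The point holds as a gap in the written analysis. SAP 10.6 specifies an unsuitable summary for continuous ECG intervals and commits to no QTcF change from baseline, although QTc prolongation is a named risk and the paired ECGs exist for that comparison. Laboratory tests and vital signs are handled properly, so the omission is specific to ECG.

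The weight is moderate. What is missing is a descriptive estimate from two time points in an uncontrolled study. Its precision would be useful in Part 2, at about 5 to 12 ms either side for a group of 20 and 3 to 8 ms for 40, and poor in Part 1 cohorts of three to six. These figures rest on the assumed SD of 10 to 25 ms and on complete pairs. The verdict concerns the text of the SAP. It does not say that the table as programmed lacks these statistics, since that shell was not available.

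**What to change.** In SAP 10.6, state that heart rate, RR, PR, QRS, QT and QTcF will be summarised with the SAP 6.6 statistics (n, mean, SD, median, minimum, maximum) for observed values at each time point and for change from baseline, by dose and, in Part 2, by RAS group. Say that baseline follows SAP 7.2. Make the shell of Table 14.3.5.3.1 match. Keep frequencies and percentages for the Normal/Abnormal classification in Table 14.3.5.3.2.

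Optionally, add a descriptive count of patients by QTcF category, with the categories fixed before the data are reviewed and the correction method stated.

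The cost is a few lines of SAP text and, if the shell does not already match, one table program. No new data, visits or protocol procedures are needed.

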#### 10.7 PHYSICAL EXAMINATIONS

Full physical examinations at Screening will include examination of general appearance, skin, eyes, ears, nose, throat, head, neck, chest, lungs, heart, abdomen, back, lymph nodes, extremities, musculoskeletal, neurological examinations and other. Subsequent targeted physical exams should include body systems as appropriate.

The frequency and percentage of subjects with each examination finding ('Normal', 'Abnormal Clinically Significant', 'Abnormal Not Clinically Significant', and 'Not Done') will be tabulated for each body system by study visit and dose level treatment group for each study part. A listing of physical examination findings will also be presented.

### 10.8 ECOG PERFORMANCE STATUS

The ECOG performance status is a rating scale used to assess how a subject's disease is progressing as well as how the disease affects the daily living abilities of the subject. The score values are 0-5, where 0 indicates "fully active, able to carry on all pre-disease performance without restriction" and 5 indicates the subject has died. It will be assessed at Screening, Baseline, Study Days 8, 15, 22, 29, 36, 43, and in subjects who continue treatment, every 3 weeks or if clinically indicated thereafter.

The frequencies and percentages of subjects' ECOG performance status will be provided by study visit and dose level treatment group for each study part. A listing of ECOG performance status will also be provided.

### 10.9 BONE MARROW ASSESSMENT

Bone marrow assessments (aspiration or biopsy, cytogenetics) will be collected at prior to therapy on Day 1 and Day 22, every 2 cycles thereafter, as well as at the Final Study Visit. Bone marrow aspirate/biopsy will be examined for: adequacy, fibrosis, cellularity, iron stores, ringed sideroblasts, histiocytes, dysplasia, bone marrow differential, and myeloid to erythroid ratio. Aspirate/biopsy samples will also be examined for biomarkers of drug response, e.g. pRSK and total RSK. Cytogenetics assessments will examine for common mutations.

### 11 PHARMACOKINETIC ANALYSES

Analyses of serum concentrations collected at Baseline (Visit 2, Cycle 1) and Day 22 (Visit 5, Cycle 1). Samples will be collected prior to administration of first daily dose and then post-dosing at 0.5, 1, 2, 4, 6, 8, and  $12 \pm 2$  hours.

Descriptive statistics will be used to summarize concentration assessments and estimated PK parameters by treatment group and time point. Comprehensive data listings will also be included.

Samples for PK analysis of BVD-523 and selected metabolites will be obtained from all Part 1 subjects during their first cycle of treatment (Cycle 1). PK samples may also be obtained from additional subjects in Part 2 depending on the outcome of initial PK analysis.

Page 31

At Visit 2 (Baseline) blood samples will be collected prior to dosing, and then at 0.5, 1, 2, 4, 6, 8, and 12 ( $\pm$  2 hours) post-dose after the administration of the first dose of the first cycle. At Day 22 (Visit 5; at steady-state) blood samples will be collected prior to dosing and then, 0.5, 1, 2, 4, 6, 8, and  $12 \pm 2$  hours post-dose. Steady state refers to patients who have received at least 5 days, or 10 consecutive doses, of investigational product. If patient is not at steady state at Day 22 (Visit 5), these assessments will be rescheduled and completed at the next visit in which steady state is achieved.

Below is the list of various PK parameters that will be calculated after Dose 1 (Day 1) and at

Steady State (Day 22).

Steady State (Bay 22).					
PK	Description				
Parameter					
(plasma)					
$C_{max}$	Peak plasma concentration determined manually by visual inspection of plasma concentration vs.				
	time figures on the untransformed (linear) scale of measurement				
t max	Time to reach the peak plasma concentration determined manually by visual inspection of plasma				
	concentration vs. time figures on the untransformed (linear) scale of measurement				
$AUC_{0-12}$	Area under the plasma concentration-time curve from 0 to 12 hours postdose, calculated by linear/log				
	trapezoidal method				
AUC 0-last	Area under the plasma concentration-time curve from time 0 to time of last observation after dosing				
	calculated by linear/log trapezoidal method				
$\lambda_{\rm z}$	Terminal phase rate constant, determined by linear regression of at least 3 points on the terminal				
	phase of the log-linear plasma concentration-time curve. The correlation coefficient (r  ) for the				
	goodness of the fit of the regression line through the data points has to be 0.85 or higher for the value				
	to be considered reliable. If the WinNonlin data points are not on the linear portion of the terminal				
	slope, the data points will be selected manually prior to calculation of $\lambda_z$				
t 1/2	Terminal half-life, defined as 0.693 (ln 2) divided by $\lambda_z$				

PK concentration and PK parameters will be provided by Covance. Descriptive statistics [n, arithmetic mean, standard deviation, coefficient of variation (CV), median, minimum, maximum, geometric mean, geometric standard deviation geometric CV] will be used to summarize PK parameters by treatment. For  $t_{1/2}$  and  $t_{max}$ , regular descriptive statistics and 95% confidence intervals about the arithmetic mean will be calculated, if possible, for each dose, but not geometric mean, geometric standard deviation, and geometric CV. Refer to the Covance Sample Analysis Outline document for additional details re. the PK analyses.

A listing of blood PK concentrations and parameters will be provided.

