## 1.4 PREVIOUS HUMAN EXPERIENCE

This study will be the second study conducted with BVD-523 in humans. The first study, Protocol BVD-523-01, "Phase 1 Dose-escalation, safety, pharmacokinetic and pharmacodynamics study of BVD-523 in patients with advanced malignancies", is in progress. Twenty seven patients with advanced malignancies have been treated in the doseescalation part (Part 1) of the first-in-man Phase 1 clinical study to investigate the safety of BVD-523 and define the MTD and the recommended Phase 2 dose (RP2D). The dose escalation phase included dose levels of 10, 20, 40, 75, 150, 300, 600, 750, and 900 mg b.i.d. The MTD and RP2D of BVD-523 was established to be 600 mg b.i.d (82).

The most common adverse events included diarrhea, nausea, vomiting or constipation (89%), rash (any form), dermatitis, or pruritus (78%), fatigue (70%), decreased appetite (37%), dyspnea (33%), and anemia (26%). Pharmacokinetics were generally linear and dose proportional up to 600 mg twice a day, and BVD-523 achieved pharmacologically relevant exposure (82).

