### 5.2.5 Visit 5 (Day 22 ± 1 of Cycle 1, first day of Cycle 2)

The following procedures will be performed at Visit 5 (Day 22 of Cycle 1, Day 1 of Cycle 2):

- Review medical history including all cancer treatments received since previous visit.
- Record medications including start/stop dates, indication, dose and frequency taken after Visit 4.
- Perform and record targeted physical examination as appropriate.
- Measure and record weight in kg.
- Assess and record performance status (ECOG).
- Bone marrow aspirate and/or biopsy. Peripheral, Geimsa and Iron stained slides will be collected with each bone marrow aspirate or biopsy. Following Cycles 1 and 2, Day 22 bone marrow aspirates will be collected only every other cycle, i.e., Cycle 4, etc.
- Bone marrow cytogenetics in accordance with local pathology requirements. (Cytogenetics would preferably include at least 20 clones).
- Record vital signs. Measure body temperature, systolic / diastolic BP and pulse rate.
- Collect pre-dose blood samples for pharmacokinetic (PK), pharmacodynamic (PD), and PBMC analyses.
  - These assessments should be collected when the patient reaches steady state. Steady state refers to patients who have received at least 5 days, or 10 consecutive doses, of investigational product. If patients are not at steady state, these assessments will be rescheduled and completed at the next visit in which steady state is achieved.
- Collect blood samples for blood chemistries, hematology and creatinine clearance.
- Collect urine samples for urinalysis.
- Perform urine pregnancy test for female patients who are not postmenopausal or surgically sterile. If urine test is positive, collect blood for a serum pregnancy test. If
serum pregnancy test is positive, withdraw patient from study and contact Medical Monitor.

- Administer BVD-523 and dispense drug supply for self-dosing for Cycle, if appropriate, and remind patient of dosing instructions.
- Collect post-dose blood samples for pharmacokinetic (PK), pharmacodynamic (PD), and PBMC analyses.
  - These assessments should be collected when the patient reaches steady state. Steady state refers to patients who have received at least 5 days, or 10 consecutive doses, of investigational product. If patients are not at steady state, these assessments will be rescheduled and completed at the next visit in which steady state is achieved.
- Assess and record disease status (every 2 cycles).
- Obtain all unused study drug from patient.

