# 8 TREATMENT

The safety and PK of BVD-523 will be tested in sequentially increasing doses starting at 300 mg twice daily, initially in patient cohorts of 3 patients (for tabular summary, see Table 3.2). Dose escalations of BVD-523 will occur in 100% increments in cohorts until one patient experiences a study related  $\geq$  Grade 2 toxicity (excluding alopecia or diarrhea), after which dose increases will be  $\leq$  50%. If one patient in a 3 patient cohort experiences a DLT as defined in Table 3.2, up to 3 additional patients will be treated at this dose level. If more than one DLT occurs in  $\leq$  6 patients, this dose level will be defined as the non-tolerated dose and dose escalation will be stopped.

Doses will not be escalated unless the patient(s) receiving the highest current dose have been observed for at least 3 weeks and dose-limiting side effects have been reported in less than 2 of 6 patients assigned to a given dose. Before each escalation, Clinical Investigators will be consulted to ensure that all involved agree with the escalation decision. Once the RP2D has been identified, up to 40 additional patients with pre-defined genetic types will be treated at this dose in Part 2.

Patients experiencing DLT or unacceptable toxicity will have their treatment interrupted until the toxicity returns to  $\leq$  Grade 1 or pre-treatment baseline (whichever is more severe). Resumption of BVD-523 treatment may then be at the next lower dose level where the safety profile has previously been established or between the dose level yielding unacceptable toxicity and the previous dose level, aligning with capsule dose availability.

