# 2 STUDY OBJECTIVES, TREATMENTS, AND ENDPOINTS

#### 2.1 STUDY OBJECTIVES

## 2.1.1 Primary Objectives

The primary objectives of the study are:

- To determine the safety and tolerability of BVD-523 in subjects with Acute Myelogenous Leukemia (AML) or Myelodysplastic Syndromes (MDS) by determining the dose-limiting toxicities (DLT), maximum tolerated dose (MTD), and the recommended Phase 2 Dose (RP2D).
- To determine the pharmacokinetic profile of BVD-523 and selected metabolites in subjects with AML or MDS.

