### 2.2 TREATMENT GROUPS

This Phase 1/2 study is single-arm.

In Phase 1 (Dose Escalation) the treatment group is subjects treated with orally administered BVD-523 BID.

In Phase 2 (Cohort Expansion) the treatment group is subjects treated with orally administered BVD-523 BID at the RP2D in one of two groups: RAS mutant positive or RAS mutant negative.

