## 2.3.2 Secondary Endpoints

Secondary endpoints are:

- Pharmacokinetic (PK) profile of BVD-523 and selected metabolites
- Progression Free Survival (PFS) and Duration of Response (DOR) in subjects achieving Complete Response (CR) or Complete Response with incomplete platelet response (CRp)

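### SAP 11 does not define which dose steady-state PK is summarised by, and its only stated PK intervals are arithmetic-mean intervals for tmax and t1/2, with none for AUC0-12 or Cmax

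*SAP*

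**What the plan says.** SAP 2.1.1 makes PK a primary objective: "To determine the pharmacokinetic profile of BVD-523 and selected metabolites in subjects with AML or MDS". SAP 2.3.2 then lists "Pharmacokinetic (PK) profile of BVD-523 and selected metabolites" among the secondary endpoints.

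SAP 11 names the grouping for PK in three ways. The opening statement is "Descriptive statistics will be used to summarize concentration assessments and estimated PK parameters by treatment group and time point". The paragraph after the parameter table summarises parameters by treatment. For t1/2 and tmax alone, "95% confidence intervals about the arithmetic mean will be calculated, if possible, for each dose". Geometric summaries are expressly left out for those two parameters. The other parameters get arithmetic and geometric descriptive statistics without an interval. Further PK detail is referred to an outline document held by the bioanalytical vendor, which is not among the documents.

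SAP 2.2 supplies the definition that the grouping depends on: "In Phase 1 (Dose Escalation) the treatment group is subjects treated with orally administered BVD-523 BID". In Part 2 the groups are RAS positive and RAS negative.

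Three provisions let the dose behind a steady-state profile differ from the one first assigned, or differ within a group:
- After a DLT or unacceptable toxicity, Protocol 8 says: "Resumption of BVD-523 treatment may then be at the next lower dose level where the safety profile has previously been established".
- Protocol 5.2.5 says of the Day 22 samples: "If patients are not at steady state, these assessments will be rescheduled and completed at the next visit in which steady state is achieved". Steady state there means 5 days or 10 consecutive doses of product; an unchanged dose is not required.
- Under Protocol 10.1.2, a DLT rate above 33% in a Part 2 cohort leads to later patients receiving less than the initial RP2D.

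**The concern.** A steady-state AUC or Cmax can be interpreted only against the dose that produced it. If a patient who was reduced for toxicity stays in the summary of the original cohort, that cohort's mean exposure falls for a reason unrelated to the assigned dose. If a RAS group contains patients treated before and after a lowered Part 2 dose, its mean describes neither dose. SAP 11 does not tell the programmer which way to go, and the PK population in SAP 5.5 carries no dose condition.

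The intervals are on the wrong parameters and the wrong scale. Exposure, which Protocol 3.1.4.3 allows as part of the RP2D rationale, has no interval. tmax, which in practice takes only the scheduled sampling times, and t1/2, which is positive and typically right-skewed, get symmetric intervals about an arithmetic mean. With cohorts based on 3 patients, such an interval can include negative times.

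At stake is how a primary objective is reported, and the PK input to any revision of the RP2D. SAP 5.2 already names 600 mg as that dose, so the first choice of RP2D is not in question here.

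**Working it through.** The plan states no PK sample size, precision target or CV, so there is no PK figure of its own to reproduce.

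**Inputs**
- Cohort size: 3, enlarged to 6 or more (SAP 3.1); Part 2 groups of at most 20.
- Linearity: "Pharmacokinetics were generally linear and dose proportional up to 600 mg twice a day" (Protocol 1.4, from the solid-tumour study).
- Sampling times: pre-dose and 0.5, 1, 2, 4, 6, 8 and 12 h (SAP 11).
- Half-life: 2-4 h across animal species (Protocol 1.5.3); no human value is given.
- Assumed: a resumed dose of one half, with two thirds as an alternative; a one-sample t interval, since the SAP gives no formula; between-patient CVs of 30% to 80%.

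**Mixed doses in one summary**

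If k of n patients are sampled at a fraction r of the cohort dose and exposure is proportional to dose, the geometric mean is multiplied by r^(k/n). For k=1 the arithmetic mean is multiplied by (n-1+r)/n.
- n=3, r=0.5: 0.5^(1/3) = 0.794, a fall of 21% (arithmetic: 2.5/3 = 0.833, a fall of 17%).
- n=6, r=0.5: 0.5^(1/6) = 0.891, a fall of 11% (arithmetic: 5.5/6 = 0.917, a fall of 8%).
- r=2/3: 0.874 at n=3 and 0.935 at n=6, falls of 13% and 7%.
- n=20, r=0.5: 0.5^(1/20) = 0.966, a fall of 3%. A lowered Part 2 dose is a different case, because k can then be much larger than 1.

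**Arithmetic-mean intervals**

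The lower limit is mean - t(0.975, n-1) × SD/√n. It is negative exactly when the observed CV = SD/mean exceeds √n / t(0.975, n-1).
- n=3: 1.732/4.303 = 0.403.
- n=6: 2.449/2.571 = 0.953.
- n=20: 4.472/2.093 = 2.14.

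Examples at n=3, with half-width 2.484 × SD:
- tmax of 1, 2, 4 h: mean 2.33, SD 1.53, interval -1.5 to 6.1 h.
- tmax of 2, 4, 4 h: mean 3.33, SD 1.15, interval 0.5 to 6.2 h.
- tmax of 2, 2, 2 h: an interval of zero width.
- t1/2 of 2, 3, 4 h: mean 3.0, SD 1.0, interval 0.5 to 5.5 h.

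For simulated log-normal data (400,000 samples per setting), the share of intervals with a negative lower limit is as follows.

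| True CV (assumed) | n=3 | n=6 |
|---|---|---|
| 30% | 14% | 0% |
| 40% | 31% | 0% |
| 50% | 46% | 0.6% |
| 80% | 70% | 10% |

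**After the change**

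A log-scale interval is the geometric mean divided and multiplied by exp(t × s/√n), with s = √ln(1+CV²). It cannot go below zero. At CV 40%, s = 0.385. The factor is exp(2.484 × 0.385) = 2.60 at n=3 and exp(1.049 × 0.385) = 1.50 at n=6. At CV 80% the factors are 5.74 and 2.09.

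**The case against.** A reader might infer that the SAP ignores dose and would pool all Part 1 dose levels in one PK summary. The documents do not support that. SAP 11 gives its two intervals separately by dose, SAP 10.2, 10.7 and 10.8 combine dose level with treatment group, and Protocol 10.3.7 sorts the concentration listing by dose. SAP 2.2 describes a single-arm study and is not an instruction to pool. The defect is an undefined grouping.

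Intra-patient escalation is a weak route to a mismatch. Protocol 3.1.2 limits it to a dose at which at least 3 patients have completed a cycle, and Protocol 3.1.3 starts a cohort only after the previous one has finished Cycle 1. In normal sequence no higher cleared dose exists at a patient's Day 22. The exceptions are patients added late to a lower cohort and profiles rescheduled well beyond Day 22. The routes that remain are reduction after toxicity, rescheduling and a lowered Part 2 dose. Half-dose resumption is an assumption, since Protocol 8 also allows doses between levels.

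The current SAP mainly updates the Part 2 shells, and the PK table it lists is a Part II table. With 20 profiles per group a negative limit would need a CV above 214%. That holds if everyone is sampled. However, SAP 11 makes Part 2 sampling conditional on the first PK results, while Protocol 6.9.1 samples all patients in Cycle 1, so the number is not fixed. The Part 1 text also remains in force.

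Median, minimum and maximum are already planned for tmax, and a log-scale interval for AUC or Cmax can be computed from the planned n, geometric mean and geometric SD. This makes the change cheap, but it does not put an interval for exposure in the plan.

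The external PK outline may settle dose handling or add intervals. The statement about which intervals exist is therefore confirmed for the SAP alone.

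**Conclusion.** The point holds as a gap in definition and a poor choice of interval.

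**Grouping.** SAP 11 does not say whether steady-state PK is summarised by assigned dose or by dose taken, and the definition it relies on in SAP 2.2 contains no dose in either part. With linear PK and a half dose, one affected patient lowers the geometric mean by about 21% at n=3 and 11% at n=6. At a two-thirds dose the falls are 13% and 7%. How often this will happen cannot be read from the documents. First-dose (Day 1) profiles are unaffected by an individual patient's later dose change.

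**Intervals.** The only PK intervals stated in the SAP are for the arithmetic means of tmax and t1/2; AUC0-12 and Cmax have none. A reader might infer that these intervals will fall below zero at cohort size 3. That is conditional. It needs an observed CV above about 40%, assumes a t interval, and the documents give no human CV. It is plausible for tmax on this coarse sampling schedule and unlikely for t1/2 if human values lie within the animal range of 2-4 h. At n=6 the threshold is about 95%, so negative limits are uncommon there.

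PK observations may enter the RP2D rationale but do not determine it. The main consequence is for the reporting of a primary objective.

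**What to change.** Amend SAP 11 as follows:
- Group each PK profile by the dose taken over the steady-state run-in (the preceding 5 days or 10 doses), or dose-normalise AUC and Cmax. Use one term for the grouping throughout, and in Part 2 show dose within RAS group.
- Flag every profile with a dose change inside the run-in, and state how it enters the summary.
- Report tmax as median (min, max), without an interval based on the mean.
- Give 95% intervals for the geometric means of AUC0-12, Cmax and t1/2, computed on the log scale and back-transformed.
- Check the external PK outline for consistency with these rules.

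The cost is SAP wording and minor programming. Dose history is already planned as Listing 16.2.5.3, so no new data are needed and no dosing rule changes. The limitation is that intervals at n=3 stay wide: at a CV of 40% the factor is still 2.6 in each direction.
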